3. PARTICIPANT SELECTION

3.1 Eligibility Criteria

- 3.1.1 Histologically confirmed liposarcoma, leiomyosarcoma, or undifferentiated/unclassified pleomorphic sarcoma, or other sarcomas (that have been reported to respond to immunotherapy such as, but not limited to, alveolar soft part sarcoma, cutaneous angiosarcoma, mismatch repair deficiency sarcomas, after review by the principal investigator and treating physician) by a Dana-Farber Cancer Institute, Brigham and Women's Hospital or Massachusetts General Hospital pathologist.

Alternative terms for undifferentiated/unclassified pleomorphic sarcomas meeting inclusion criteria include but are not limited to the following:

pleomorphic undifferentiated sarcoma
 unclassified spindle cell sarcoma
 spindle cell sarcoma not otherwise specified
 pleomorphic spindle cell sarcoma
 pleomorphic fibroblastic sarcoma
 undifferentiated high-grade pleomorphic sarcoma
 pleomorphic sarcoma with prominent inflammation
 pleomorphic sarcoma with giant cells
 malignant fibrous histiocytoma (including storiform-pleomorphic and inflammatory subtypes)
 fibrosarcoma
 myxofibrosarcoma
 extraskeletal osteosarcoma (soft tissue sarcoma with osteoid differentiation)

- 3.1.2 Participants must have measurable disease, defined as at least one lesion that can be accurately measured in at least one dimension (longest diameter to be recorded for non-nodal lesions and short axis for nodal lesions) as ≥ 20 mm with conventional techniques or as ≥ 10 mm with spiral CT scan, MRI, or calipers by clinical exam. See Section 11 for the evaluation of measurable disease.
- 3.1.3 Participants must have received at least one prior line of chemotherapy. No limit on prior lines of therapy.
- 3.1.4 Age ≥ 18 years.
- 3.1.5 ECOG performance status of 0 or 1 (see Appendix A).
- 3.1.6 Participants must have normal organ and marrow function as defined below:
- leukocytes $\geq 3,000/\text{mcL}$
 - absolute neutrophil count $\geq 1,500/\text{mcL}$
 - platelets $\geq 100,000/\text{mcL}$
 - Hemoglobin ≥ 8 g/dL within the first 2 weeks prior to the first dose of study drugs, transfusion is allowed.
 - total bilirubin $\leq 1.5 \times$ institutional upper limit of normal (ULN)
(except participants with Gilbert Syndrome, who can have total bilirubin < 3.0 mg/dL)
 - AST(SGOT)/ALT(SGPT) $< 2.5 \times$ ULN in a participant with no documented liver metastases; ALT and AST $< 5.0 \times$ ULN in a participant with documented liver metastases
 -
 - creatinine $\leq 1.5 \times$ ULN
OR

- creatinine clearance ≥ 50 mL/min/1.73 m² for participants with creatinine levels above institutional normal (using the Cockcroft-Gault Formula below):

$$\text{Female CrCl} = \frac{(140 - \text{age in years}) \times \text{weight in kg} \times 0.85}{72 \times \text{serum creatinine in mg/dL}}$$

$$\text{Male CrCl} = \frac{(140 - \text{age in years}) \times \text{weight in kg}}{72 \times \text{serum creatinine in mg/dL}}$$

- 3.1.7 The effects of eribulin and pembrolizumab on the developing human fetus are unknown. For this reason, women of child-bearing potential (WOCBP) and men must agree to use adequate contraception (hormonal or barrier method of birth control; abstinence) prior to study entry and for the duration of study participation. A male participant must agree to use a contraception as detailed in Appendix G of this protocol during the treatment period and for at least 20 weeks, corresponding to the time needed to eliminate any study treatments, plus an additional 120 days (a spermatogenesis cycle) after the last dose of study treatment. A female participant is eligible to participate if she is not pregnant (see Appendix G), not breastfeeding, and at least one of the following conditions applies:

- a.) Not a woman of childbearing potential (WOCBP) as defined in Appendix G
- OR
- b.) A WOCBP who agrees to follow the contraceptive guidance in Appendix G during the treatment period and for at least 20 weeks plus an additional 30 days (a menstruation cycle) after the last dose of study treatment.

WOCBP should use an adequate method to avoid pregnancy for at least 20 weeks plus an additional 30 days after the last dose of investigational drug. Women of childbearing potential must have a negative serum pregnancy test within 72 hours prior to the start of Eribulin and Pembrolizumab. Women must not be breastfeeding. Women who are not of childbearing potential (*i.e.*, who are postmenopausal or surgically sterile) do not require contraception. Women of childbearing potential (WOCBP) is defined as any female who has experienced menarche and who has not undergone surgical sterilization (hysterectomy or bilateral oophorectomy) or who is not postmenopausal. Menopause is defined clinically as 12 months of amenorrhea in a woman over 45 in the absence of other biological or physiological causes. In addition, women under the age of 55 must have a documented serum follicle stimulating hormone (FSH) level less than 40 mIU/mL.

- 3.1.8 Ability to understand and the willingness to sign a written informed consent document.

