4. REGISTRATION PROCEDURES

4.1 General Guidelines for DF/HCC Institutions

Institutions will register eligible participants in the Clinical Trials Management System (CTMS) OnCore. Registrations must occur prior to the initiation of protocol therapy. Any participant not registered to the protocol before protocol therapy begins will be considered ineligible and registration will be denied.

An investigator will confirm eligibility criteria and a member of the study team will complete the protocol-specific eligibility checklist.

Following registration, participants may begin protocol therapy. Issues that would cause treatment delays should be discussed with the Overall PI. If a participant does not receive protocol therapy following registration, the participant's registration on the study must be canceled. Registration cancellations must be made in OnCore as soon as possible.

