5.2 Pre-Treatment Criteria

5.2.1 Cycle 1, Day 1

Criteria to treat on Cycle 1 Day 1 (Patient does not need to re-meet full eligibility criteria):

- Absolute neutrophil count $>1500/\text{mcL}$
- Platelets $>100,000/\text{mcL}$
- ALT and AST $<2.5 \times \text{ULN}$ in a participant with no documented liver metastases; ALT and AST $<5.0 \times \text{ULN}$ in a participant with documented liver metastases
- Total bilirubin $<1.5 \times \text{ULN}$ ($2.0 \times \text{ULN}$ in a participant with well documented Gilbert's syndrome)

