AST and ALT elevation or Increased bilirubin	Grade 2	Withhold	
 • Administer corticosteroids (initial dose of 0.5- 1 mg/kg prednisone or equivalent) followed by taper 	
 • Monitor with liver function tests (consider weekly or more frequently until liver enzyme value returned to baseline or is stable)

	Grade 3 or 4	Permanently discontinue	
 Administer corticosteroids (initial dose of 1-2 mg/kg prednisone or equivalent) followed by taper 	
Type 1 diabetes mellitus (T1DM) or Hyperglycemia	Newly onset T1DM or Grade 3 or 4 hyperglycemia associated with evidence of β -cell failure	Withhold	
 Initiate insulin replacement therapy for participants with T1DM Administer anti-hyperglycemic in participants with hyperglycemia 	
 Monitor participants for hyperglycemia or other signs and symptoms of diabetes.
Hypophysitis	Grade 2	Withhold	
 Administer corticosteroids and initiate hormonal replacements as clinically indicated. 	
 Monitor for signs and symptoms of hypophysitis (including hypopituitarism and adrenal insufficiency)
	Grade 3 or 4	Withhold or permanently discontinue ¹		
Hyperthyroidism	Grade 2	Continue	
 Treat with non-selective beta-blockers (eg, propranolol) or thionamides as appropriate 	
 Monitor for signs and symptoms of thyroid disorders.
	Grade 3 or 4	Withhold or permanently discontinue ¹		
Hypothyroidism	Grade 2-4	Continue	
 Initiate thyroid replacement hormones (eg, levothyroxine or liothyronine) per standard of care 	
 Monitor for signs and symptoms of thyroid disorders.
Nephritis and Renal dysfunction	Grade 2	Withhold	
 Administer corticosteroids (prednisone 1-2 mg/kg or equivalent) followed by taper. 	
 Monitor changes of renal function
	Grade 3 or 4	Permanently discontinue		
Myocarditis	Grade 1 or 2	Withhold	
 Based on severity of AE administer corticosteroids 	
 Ensure adequate evaluation to confirm etiology and/or exclude other causes
	Grade 3 or 4	Permanently discontinue		

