Hepatic Adverse Event Management Algorithm

Rule out non-inflammatory causes. If non-inflammatory cause, treat accordingly and continue I-O therapy. Consider imaging for obstruction.

Grade of Liver Test Elevation (NCI CTCAE v4)	Management	Follow-up
Grade 1 AST or ALT > ULN to 3.0 x ULN and/or Total bilirubin (T. bili) > ULN - 1.5 x ULN	
 Continue I-O therapy per protocol 	
 Continue liver function tests (LFT) monitoring per protocol If worsens: Treat as Grade 2 or 3-4
Grade 2 AST or ALT > 3.0 to ≤ 5 x ULN and/or T. bili > 1.5 to ≤ 3 x ULN	
 Delay I-O therapy per protocol Increase frequency of monitoring to every 3 days 	
 If returns to baseline: Resume routine monitoring, resume I-O therapy per protocol If elevations persist > 5-7 days or worsen: 0.5-1 mg/kg/day methylprednisolone or oral equivalent and when LFT returns to grade 1 or baseline, taper steroids over at least 1 month, consider prophylactic antibiotics for opportunistic infections, and resume I-O therapy per protocol
Grade 3-4 AST or ALT > 5 x ULN and/or T.bili > 3 x ULN	
 Discontinue I-O therapy* Increase frequency of monitoring to every 1-2 days 1.0 to 2.0 mg/kg/day methylprednisolone IV or IV equivalent** Add prophylactic antibiotics for opportunistic infections Consult gastroenterologist 	
 If returns to grade 2: Taper steroids over at least 1 month If does not improve in >3-5 days, worsens or rebounds: Add mycophenolate mofetil 1 gram (g) twice daily (BID) If no response within an additional 3-5 days, consider other immunosuppressants per local guidelines

[figure not shown]
Patients on IV steroids may be switched to an equivalent dose of oral corticosteroids (e.g. prednisone) at start of tapering or earlier, once sustained clinical improvement is observed. Lower bioavailability of oral corticosteroids should be taken into account when switching to the equivalent dose of oral corticosteroids.

*I-O therapy may be delayed rather than discontinued if AST/ALT ≤ 8 x ULN and T.bili ≤ 5 x ULN.

**The recommended starting dose for grade 4 hepatitis is 2 mg/kg/day methylprednisolone IV.

Neurological Adverse Event Management Algorithm

[figure not shown]

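### The hepatic rules conflict on stopping pembrolizumab at Grade 3–4, on steroids and resumption at Grade 2, and on the Gilbert bilirubin limit

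*Combined protocol and SAP*

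**What the plan says.** Liver-test rules stand in five places.

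- **Entry (Section 3.1.6).** AST/ALT must be below 2.5 × ULN, or below 5.0 × "ULN in a participant with documented liver metastases". Total bilirubin may be at most 1.5 × ULN, "except participants with Gilbert Syndrome, who can have total bilirubin" below 3.0 mg/dL.
- **Dosing (Sections 5.2.1–5.2.3).** The AST/ALT limits are the same as at entry. Bilirubin must be below 1.5 × ULN, or 2.0 × ULN "in a participant with well documented Gilbert's syndrome". Section 5.2.3 lets a new cycle begin once non-hematologic toxicity is back at baseline or below Grade 2.
- **Table 4.1 (Section 6.2).** It covers immune-related events, graded by CTCAE v5.0. In the row "AST and ALT elevation or Increased bilirubin", Grade 2 means withhold and give corticosteroids, and Grade 3 or 4 means permanent discontinuation. The table's general instructions allow pembrolizumab to resume once the event is Grade 1 or 0 and steroids have been tapered.
- **Section 5.8.** Pembrolizumab is discontinued in anyone given steroids for an event of Grade 3 or higher; only thyroiditis and skin rash are excepted.
- **Appendix B, hepatic algorithm.** Its grading column is headed "Grade of Liver Test Elevation (NCI CTCAE v4"). Grade 2 is AST/ALT above 3.0 and up to 5 × ULN, or bilirubin above 1.5 and up to 3 × ULN. Therapy is delayed, and steroids follow only if the elevation lasts more than 5–7 days or worsens. Return to baseline is enough to resume. Grade 3–4 (AST/ALT above 5 × ULN or bilirubin above 3 × ULN) means discontinue, but a footnote permits a delay instead if AST/ALT is at most 8 × ULN and bilirubin at most 5 × ULN.

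**The concern.** An investigator with one liver result can reach different actions depending on which page is read: stop pembrolizumab for good or delay it, start steroids at once or wait, resume at the entry value or not. Section 5.3.4 lets a participant continue on eribulin alone after pembrolizumab is stopped for toxicity. Exposure to the combination under test can therefore turn on an unresolved conflict in the text. Rates of holding, steroid use and discontinuation, which feed the tolerability objective in Section 1.3.2, would depend on it too. Separately, a participant can satisfy the entry criteria and then be undosable on the first day.

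**Working it through.** The check sets thresholds side by side. Only Appendix B prints grade cut-offs for liver tests. Table 4.1 relies on CTCAE v5.0, which the documents do not reproduce, so steps 1 and 2 assume that Appendix B's cut-offs, as multiples of ULN, also fix the grade in Table 4.1.

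**1. Grade 3–4.** Take an immune-related rise in AST/ALT to more than 5 and at most 8 × ULN, with bilirubin at most 5 × ULN.

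| Source | Action on pembrolizumab |
|---|---|
| Table 4.1 | Permanent discontinuation; no delay option |
| Section 5.8, if steroids were given | Discontinuation; no hepatic exception |
| Appendix B footnote | Delay permitted |

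The conflict arises after the cause has been judged inflammatory, so the instruction to rule out other causes cannot resolve it.

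**2. Grade 2.**
- *Steroids.* Table 4.1 pairs them with withholding. Appendix B reserves them for an elevation that persists beyond 5–7 days or worsens.
- *Version.* Section 6 and Table 4.1 name v5.0; Appendix B names v4.
- *Resumption.* Take a participant with liver metastases who enters at AST 4.0 × ULN, which Sections 3.1.6 and 5.2 allow (4.0 < 5.0). AST rises, pembrolizumab is held for a suspected immune-related event, and AST returns to 4.0 × ULN. Appendix B and Section 5.2.3 accept this as baseline. Under Table 4.1 the value is still Grade 2 (3.0 < 4.0 ≤ 5), so the Grade 1 or 0 condition is not met. Section 5.8 asks for Grade 0 or baseline after hepatitis but explains baseline as an initial grade of at most 1, which does not clearly cover this participant. The same follows for any entry value above 3.0 and below 5.0 × ULN.

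**3. Gilbert syndrome.** Entry limit: 3.0 mg/dL. Dosing limit: 2.0 × ULN. A gap exists when 2.0 × ULN < 3.0, that is, when ULN < 3.0/2.0 = 1.5 mg/dL. ULN is varied because the documents give none.

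| Assumed ULN (mg/dL) | Dosing limit (mg/dL) | Eligible but not dosable (mg/dL) |
|---|---|---|
| 1.0 | 2.0 | from 2.0 to below 3.0 |
| 1.2 | 2.4 | from 2.4 to below 3.0 |
| 1.3 | 2.6 | from 2.6 to below 3.0 |
| 1.5 | 3.0 | none |

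Section 5.2 gives no separate inequality sign for the 2.0 × ULN figure, so the status of a value exactly at that limit is unclear.

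**4. Inequality signs (minor).** ANC 1,500/mcL and platelets 100,000/mcL are minima reached with ≥ in Section 3.1.6 but must be exceeded in Section 5.2.1. Bilirubin 1.5 × ULN passes entry (≤) and fails Day 1 (<).

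**5. Primary decision rule.** For at least 9 progression-free of 19, the exact binomial gives P(X ≥ 9 | 0.30) = 0.0839 and P(X ≥ 9 | 0.60) = 0.9115. This reproduces the stated 91% power within the 10% one-sided error. No hepatic limit enters the calculation.

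**The case against.** A reader might infer that admitting participants with liver metastases at 3–5 × ULN contradicts the hold rules outright, so that they sit on hold from the start. The documents do not support this. Entry and dosing limits for AST/ALT are identical. Table 4.1 concerns immune-related events, and Section 6.2 asks that other causes be excluded. Appendix B continues therapy when the cause is non-inflammatory. Section 5.2.3, Table 4.2 and Appendix B accept baseline. What remains is narrower: the resumption problem after a participant has been held.

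Nor can an unchanged AST/ALT value lead to permanent discontinuation. Every admitted value is below 5.0 × ULN, and Appendix B Grade 3 begins above 5. A value must rise before step 1 applies.

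A reader might also infer that undosable participants drop out of an arm of 19, since Section 4.1 says: "If a participant does not receive protocol therapy following registration, the participant's registration on the study must be canceled". But that section first asks that issues causing delay be discussed with the Overall PI, and Section 10 gives a ±3-day window. One failed Day 1 test need not end in cancellation. Section 13.9.3 already foresees a possible exception for untreated participants in the response analysis. The tension with the intent-to-treat statement in Section 13.9.2 is secondary here.

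Other objections carry some weight. The text after Table 4.9 says that the algorithms' waiting period must not delay steroids that are clinically indicated. This softens the timing difference but does not turn a conditional step into the routine one in Table 4.1. CTCAE v5.0 may itself address abnormal baselines, which cannot be checked from these documents. Section 5.2.1 says full eligibility need not be met again on Day 1, but bilirubin is among the criteria that it does list. The sign differences affect only someone exactly at a limit, and a lost underline in the PDF reading cannot be excluded.

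**Conclusion.** The point holds for three conflicts: the action on pembrolizumab at Grade 3–4; steroid timing, grading version and resumption at Grade 2; and the Gilbert bilirubin limit. The first spans AST/ALT above 5 and up to 8 × ULN with bilirubin at most 5 × ULN. The resumption problem concerns participants with liver metastases who entered above 3.0 and below 5.0 × ULN and were then held for a suspected immune-related event. Both rest on applying Appendix B's cut-offs to Table 4.1. The Gilbert gap exists only if the ULN is below 1.5 mg/dL and affects only those above 2.0 × ULN, not every Gilbert participant. The sign mismatch is minor.

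The documents give no basis for estimating how many participants are affected, and no effect on the primary result is shown. The matter still deserves correction, because the conflicting texts decide whether a participant is dosed, held, given steroids or stopped.

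**What to change.** Reconcile Sections 3.1.6, 5.2.1–5.2.3 and 5.8, Table 4.1 and the Appendix B hepatic algorithm so that each of the following is stated once and applies throughout:

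- one Gilbert bilirubin limit in one unit, and one set of inequality signs for entry and dosing;
- one CTCAE version;
- one action on pembrolizumab, and one steroid instruction, for each hepatic grade;
- one resumption rule, stating whether participants who enter above ULN are graded against ULN or against their entry value.

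Which limits and actions apply is the sponsor's clinical decision; none is proposed here.

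The cost is protocol wording, with no new test. Depending on the limits chosen, a few participants with liver metastases or Gilbert syndrome might no longer be eligible. If treatment is already complete, the report should state which hepatic rule was applied in practice.

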2.5.2.3 Pharmacokinetics clinical development of Eribulin

In clinical studies, eribulin 's PK is characterized by a rapid distribution phase, with a prolonged elimination phase after intravenous infusion. The disposition of eribulin follows linear kinetics over the dose range studied (0.25mg/m²- 4.0mg/m²). It has low plasma clearance, with a mean clearance=1.16-2.42 L/hr/m², a large mean volume of distribution at steady state (43-114 L/m²) and a half-life of elimination of 40 hours. The human plasma protein binding of eribulin occurs at concentrations of 100ng/mL to 1.000ng/mL and ranges from 49% to 65%. Eribulin exposure after multiple doses is comparable to a single dose, with no accumulation of eribulin with weekly administration. As expected based on work in pre-clinical models, metabolism is a minor component of eribulin clearance. Metabolites represent less than 0.6% of parent compound in plasma. Renal elimination is also a minor route of eribulin excretion, with less than 10% of drug excreted unchanged in urine. Most of excretion of eribulin is fecal and unchanged. It is unknown if eribulin is excreted into human milk.⁶⁴

Eribulin does not induce or inhibit hepatic CYP3A4 activity at clinically relevant concentrations. Concomitant administration of ketoconazole, a CYP3A4 inhibitor, or rifampicin, a CYP3A4 inducer, had no effect on exposure to eribulin. Eribulin does not induce or inhibit CYP1A, CYP2C9, CYP2C19, CYP2D6 activity at clinically relevant concentrations.⁶⁴

Hepatic impairment may decrease the clearance of eribulin and prolong the elimination half-life, resulting in increased exposure to eribulin. As such, it is proposed that the eribulin dose in patients with moderate hepatic impairment should be adjusted. No studies for patients with severe hepatic impairment have been performed.⁶⁴

Moderate renal impairment (CrCL 30-50 mL/min) may also impact the clearance of eribulin, resulting in increased exposure. As such, it is proposed that eribulin dose in patients with moderate renal impairment should be adjusted. No studies for patients with severe renal impairment have been performed.⁶⁴

Population PK analyses based on Phase 1 and 2 studies showed that eribulin meslyate's clearance is affected by body weight, serum albumin, alkaline phosphatase

and bilirubin. The effects of age, gender, race and concomitant medications (CYP3A4 inhibitors and inducers) on clearance were not found to be significant.⁶⁴

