Unchanged eribulin was the major circulating species in plasma following administration of ¹⁴C-eribulin to participants. Metabolite concentrations represented <0.6% of parent compound, confirming that there are no major human metabolites of eribulin.

Cytochrome P450 3A4 (CYP3A4) negligibly metabolizes eribulin *in vitro*.

Excretion

Eribulin is eliminated primarily in feces unchanged. After administration of ¹⁴C-eribulin to participants, approximately 82% of the dose was eliminated in feces and 9% in urine. Unchanged eribulin accounted for approximately 88% and 91% of total eribulin in feces and urine, respectively.

Drug Interaction Studies

Effect of Strong Inhibitors or Inducers of CYP3A4 on Eribulin: The effect of a strong CYP3A4 inhibitor and a P-gp inhibitor, ketoconazole, on the PK of eribulin was studied in a crossover trial of 12 participants with advanced solid tumors. No clinically relevant PK interaction was observed when eribulin was administered with or without ketoconazole (the geometric mean ratio of the AUC: 0.97; 90% CI: 0.83, 1.12).

The effect of a CYP3A4 inducer, rifampin, on the PK of eribulin was studied in a crossover trial of 14 participants with advanced solid tumors. No clinically relevant PK interaction was observed when eribulin was administered with or without rifampin (the geometric mean ratio of the AUC: 1.10; 90 CI%: 0.91, 1.34).

Effect of Eribulin on CYP Substrates: Eribulin shows no induction potential for CYP1A, CYP2B6, CYP2C9, CYP2C19, and CYP3A in primary human hepatocytes. Eribulin inhibits CYP3A4 activity in human liver microsomes, but it is unlikely that eribulin will substantially increase the plasma levels of CYP3A4 substrates. No significant inhibition of CYP1A2, CYP2C9, CYP2C19, CYP2D6, or CYP2E1 was detected with eribulin concentrations up to 5 µM in pooled human liver microsomes. In vitro drug interaction studies indicate that eribulin does not inhibit drugs that are substrates of these enzymes and it is unlikely that eribulin will affect plasma levels of drugs that are substrates of CYP enzymes.

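### Section 3.1.6 asks for no creatinine clearance when creatinine is within normal limits, and its limit is in a different unit from the formula, so some older or lighter participants can start full-dose eribulin at 30-50 mL/min

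*Combined protocol and SAP*

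**What the plan says.** The renal part of Section 3.1.6 has two lines joined by OR: creatinine at or below 1.5 x ULN, or a clearance of at least 50 mL/min/1.73 m². The second line applies "for participants with creatinine levels above institutional normal (using the Cockcroft-Gault Formula below".

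Section 2.5.2.3 gives the pharmacology: "Moderate renal impairment (CrCL 30-50 mL/min) may also impact the clearance of eribulin, resulting in increased exposure". It continues: "As such, it is proposed that eribulin dose in patients with moderate renal impairment should be adjusted". It gives no adjusted dose, and says that severe renal impairment has not been studied. The same section also states: "Renal elimination is also a minor route of eribulin excretion, with less than 10% of drug excreted unchanged in urine".

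For dosing, Sections 1.1 and 5.1 start every participant at 1.4 mg/m² on Days 1 and 8. The treatment criteria in Sections 5.2.1 to 5.2.3 list neutrophils, platelets, ALT/AST and bilirubin, but no creatinine or clearance. Section 5.2.1 adds: "Patient does not need to re-meet full eligibility criteria". Eribulin Tables 2 and 3.1 to 3.5 have no renal row; the renal row in Table 4.1 governs pembrolizumab. Section 3.1 sets no upper age limit and no minimum weight.

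**The concern.** Serum creatinine alone is a poor guide to clearance in older and lighter people, because the Cockcroft-Gault value falls with age and with low weight at the same creatinine. Section 3.1.6 uses the formula only after creatinine has already risen above normal, so it misses participants whose creatinine is normal but whose calculated clearance is low. Read literally, the OR goes further: anyone up to 1.5 x ULN qualifies on the first line and needs no calculation.

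There is a second, independent problem. The limit is indexed to 1.73 m², but the printed formula returns mL/min and the 30-50 band in Section 2.5.2.3 is also in mL/min. A small participant inside the band can pass the indexed limit even when the calculation is done.

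At stake is a full first dose of a myelosuppressive drug in some participants for whom the protocol's own background section proposes an adjusted one. Age, weight and creatinine are all collected, so the check is possible, but no step asks for it.

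**Working it through.** The plan gives no figure of its own on this point. The question is whether a clearance of 30-50 mL/min can be reached with creatinine at or below ULN.

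**Inputs.** Formula and limit of 50: Section 3.1.6. Band of 30-50 mL/min: Section 2.5.2.3. The documents give no creatinine ULN, so ranges are assumed: 0.9, 1.0 and 1.1 mg/dL for women; 1.1, 1.2 and 1.3 for men. Ages, weights and heights are illustrative.

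**Formula.** CrCl = (140 - age) x weight x k / (72 x creatinine), with k = 0.85 for women and 1 for men. Setting CrCl = 50 gives the crossing creatinine, (140 - age) x weight x k / 3600, which needs no ULN. For a woman of 75 and 55 kg: 65 x 55 x 0.85 / 3600 = 0.844 mg/dL.

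| Creatinine (mg/dL) above which CrCl < 50 mL/min | 70 y | 75 y | 80 y |
|---|---|---|---|
| Woman, 50 kg | 0.83 | 0.77 | 0.71 |
| Woman, 55 kg | 0.91 | 0.84 | 0.78 |
| Woman, 70 kg | 1.16 | 1.07 | 0.99 |
| Man, 60 kg | 1.17 | 1.08 | 1.00 |
| Man, 70 kg | 1.36 | 1.26 | 1.17 |

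**Width of the gap.** This is the assumed ULN minus the crossing value, at age 75:

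- Woman, 55 kg: 0.06, 0.16 and 0.26 mg/dL at ULN 0.9, 1.0 and 1.1.
- Woman, 70 kg: none at 0.9 or 1.0; 0.03 at 1.1.
- Man, 60 kg: 0.02, 0.12 and 0.22 mg/dL at ULN 1.1, 1.2 and 1.3.
- Man, 70 kg: none at 1.1 or 1.2; 0.04 at 1.3.

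The gap lies near the top of the normal range. The 55 kg woman of 75 has 60.3 mL/min at creatinine 0.7, 52.8 at 0.8, 46.9 at 0.9 and 42.2 at 1.0.

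**Literal OR reading only.** With creatinine at 1.5 x ULN and threshold T, the age above which clearance is below T is 140 - T x 72 x 1.5 x ULN / (weight x k). A 70 kg man is below 50 mL/min above 55, 47 and 40 years (ULN 1.1, 1.2, 1.3). A 55 kg woman is below 30 mL/min above 78, 71 and 64 years (ULN 0.9, 1.0, 1.1).

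**Unit.** The indexed limit in mL/min is 50 x BSA / 1.73: 43.4 at 1.5 m², 46.2 at 1.6, 57.8 at 2.0 and 63.6 at 2.2. The 55 kg woman of 75 at creatinine 0.9 has 46.9 mL/min. At an assumed 160 cm her BSA (Mosteller) is √(160 x 55 / 3600) = 1.563 m², and 46.9 x 1.73 / 1.563 = 51.9 mL/min/1.73 m² (53.6 at 150 cm, 50.3 at 170 cm). She is inside the band yet passes the limit as written.

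**The case against.** The pharmacological case for a renal effect is weak on the documents' own evidence. Urinary excretion is minor (Section 8.2.1: "approximately 82% of the dose was eliminated in feces and 9% in urine"). Section 2.5.2.3 lists body weight, albumin, alkaline phosphatase and bilirubin as affecting clearance; renal function is not on that list, although the section does not say whether it was tested. It also reports: "The effects of age, gender, race and concomitant medications (CYP3A4 inhibitors and inducers) on clearance were not found to be significant". Dosing per m² already lowers the milligram dose in light participants. This limits the likely effect, but Section 2.5.2.3 proposes the adjustment while reporting the minor renal route, so the two sections remain unreconciled.

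Sites could act without a written rule. Section 5.3.1 points to the package insert and to institutional standard for dose calculations. The renal statement in Section 2.5.2.3 itself cites the prescribing information, and creatinine is measured before each dose. This stands as a mitigation. But the pointer is general, states no renal rule, and sits beside a fixed dose of 1.4 mg/m² in Table 1.

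Toxicity rules also help: Day 8 blood-count criteria, skipped Day 8 doses, and the holds and reductions in Tables 3.3 and 3.4. These act only after a first full dose. Growth factor is allowed as primary prophylaxis, at the investigator's discretion.

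A reader might infer an oversight from the hepatic side, where the background makes a parallel proposal ("As such, it is proposed that the eribulin dose in patients with moderate hepatic impairment should be adjusted") and Sections 3.1.6 and 5.2 do set limits. The contrast is real but not like for like: bilirubin and alkaline phosphatase are listed covariates and fecal excretion dominates, so stricter hepatic limits are coherent in their own right.

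Finally, the background proposes adjusting the dose, not excluding the participant, and Section 3.3 aims to enter all eligible participants in a rare disease. This stands, and the fix offers a dose-based alternative.

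**Conclusion.** The gap is real on either reading of the OR. At or below ULN no clearance is required; read literally, none is required up to 1.5 x ULN. The unit of the limit does not match the formula or the band it is meant to guard. Some older or lighter participants with creatinine in the upper part of the normal range can start at 1.4 mg/m² with 30-50 mL/min.

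The size is modest. The crossing creatinines follow from the printed formula alone; the gap widths depend on the assumed ULNs, and the indexed example on an assumed height. The figures show who can enter, not how many of the 57 would.

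A reader might infer that these participants would be overdosed, or that the protocol requires a lower dose for them. The documents support neither: the renal statement is background, hedged, and gives no adjusted dose or exposure increase. Nor does the point reach the statistical design, since the primary decision rule and the sample size are unaffected. It is a participant-safety and consistency point that should be fixed because the fix is cheap.

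**What to change.** In Section 3.1.6, replace the two creatinine lines joined by OR with one criterion: Cockcroft-Gault clearance by the printed formula of at least 50 mL/min, calculated for every participant at screening. Both parts are needed, because extending the calculation while keeping the indexed unit would still pass the 55 kg woman above.

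If the sponsor prefers not to exclude in this rare disease, it can admit 30-50 mL/min and write a reduced eribulin starting dose into Section 6.1, for example the existing 1.1 mg/m² level in Table 2. That level is only an example, since the documents do not say what the adjusted dose should be. Such participants would have one further reduction left (0.7 mg/m²) before eribulin must stop.

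The cost is protocol wording and one checklist calculation from data already collected. A few older or lighter participants are screened out or start lower. Where the indexed limit now applies, the floor tightens below 1.73 m² (43.4 to 50 mL/min at 1.5 m²) and loosens above it (63.6 to 50 at 2.2 m²). Neither option adds a renal check after screening; a fall in clearance during treatment would still be left to the investigator.
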